9.2.3 Serious Adverse Events

An SAE is an AE, whether considered related to a study vaccine or not, meeting one of the following conditions:

1. Death during the period of protocol-defined surveillance
2. Life threatening: defined as an event that places a subject at immediate risk of death at the time of the event and does not refer to an event that hypothetically might have caused death were it more severe
3. Hospitalization during the period of protocol-defined surveillance: defined as at least an overnight stay in the hospital or emergency ward for treatment that would have been inappropriate if administered in the outpatient setting
4. Results in a congenital anomaly or birth defect
5. Results in a persistent or significant disability or incapacity: defined as a substantial disruption of the study subject's ability to carry out normal life functions
6. Any other important medical event that may not result in death, be life threatening, or require hospitalization, may be considered a serious AE when, based upon appropriate medical judgment, the event may jeopardize the subject and may require medical or surgical intervention to prevent one of the outcomes listed above.

9.2.4 Procedures to be Followed in the Event of Abnormal Laboratory Test Values or Abnormal Clinical Findings

The Principal Investigator or appropriate co-investigator is responsible for reporting all AE/SAEs that are observed or reported during the study, regardless of the relationship to study products. AE/SAEs, abnormal clinical laboratory test values, or abnormal clinical findings will be documented, reported, and followed appropriately.

9.3 Reporting Procedures

9.3.1 Serious Adverse Events

All SAEs will be reviewed by a study physician, recorded on the appropriate SAE form, and followed through to resolution or stabilization by a study physician. All SAEs will be reported by email, telephone or fax within 1 working day of notification of the SAE occurrence to the Principal Investigator, via a scanned PDF version of an SAE form to:

[name] [name], PhD
Deputy Director,
Sabin Vaccine Institute Product Development Partnership
[name]
[contact], Alt. [contact], [contact]
Email: [contact]

In addition, the Principal Investigator will report all SAEs that are determined to be definitely or probably related to vaccination to the Institutional Review Boards (IRBs) that approved the study

(the IRB of the George Washington University and the local IRB in Brazil) according to the IRB's reporting timelines and using the IRB-specified reporting forms, as the DMID Medical Monitor.

All local and systemic reactions not meeting the criteria for SAE will be captured on the appropriate case report form (CRF). These events will be followed to resolution.

In addition, all SAEs must be submitted within 24 hours of site awareness on an SAE form to the DMID pharmacovigilance contractor, at the following address:

DMID Pharmacovigilance Group
Clinical Research Operations and Management Support (CROMS)
[name]
[name]

SAE Hot Line: [name] (US) or [name] (outside US)
SAE FAX [contact] (US) or [name] (outside US)
SAE Email Address: [contact]

9.3.2 Regulatory Reporting for Studies Conducted Under DMID-Sponsored IND

Not Applicable

9.3.3 Regulatory Reporting for Studies Not Conducted Under DMID-Sponsored IND

Following notification from the Principal Investigator, the IND sponsor (Sabin Vaccine Institute) will report events that are both serious and unexpected that are possibly, probably, or definitely related to the vaccine, to the FDA and ANVISA (the Brazilian national regulatory agency) within the required timelines: fatal and life-threatening events within 7 calendar days (by phone, fax, or internet) and all other SAEs in writing within 15 calendar days. All SAEs not listed as possibly, probably, or definitely related will be reported to the FDA and ANVISA at least annually in a summary format.

All Adverse Events of Special Interest (AESIs; see below) will be reported to Sponsor, FDA and ANVISA according to the same procedure as for reporting SAEs, and according to the same timelines as described above.

9.3.4 Adverse Events of Special Interest (AESI)

Special attention will be paid to monitoring for the occurrence of certain adverse events termed, "**Adverse Events of Special Interest**" or AESIs. These include inflammatory and autoimmune disorders that may potentially be related to the use of an immunostimulatory adjuvant (although none have been associated with the use of GLA-AF). The occurrence of the following AESI's will be closely monitored:

-
- Neuroinflammatory disorders (optic neuritis, multiple sclerosis, demyelinating disease, transverse myelitis, Guillain-Barre syndrome, myasthenia gravis, encephalitis, neuritis, Bell's palsy)
 - Musculoskeletal disorders (systemic lupus erythematosus, cutaneous lupus, Sjogren's syndrome, scleroderma, dermatomyositis, polymyositis, rheumatoid arthritis, juvenile rheumatoid arthritis, polymyalgia, rheumatica, reactive arthritis, psoriatic arthropathy, ankylosing spondylitis, spondylarthropathy)
 - Gastrointestinal disorders (Crohn's disease, ulcerative colitis, celiac disease)
 - Metabolic diseases (autoimmune thyroiditis, Grave's or Basedow's disease, Hashimoto thyroiditis, insulin-dependent diabetes mellitus, Addison's disease)
 - Skin disorders (psoriasis, vitiligo, Raynaud's phenomenon, erythema nodosum, autoimmune bullous skin diseases)
 - Others (autoimmune hemolytic anemia, idiopathic thrombocytopenic purpura, antiphospholipid syndrome, temporal arteritis, Behcet's syndrome, pernicious anemia, autoimmune hepatitis, primary biliary cirrhosis, primary sclerosing cholangitis, autoimmune glomerulonephritis, autoimmune uveitis, autoimmune cardiomyopathy, sarcoidosis, Stevens-Johnson syndrome).
 - Vasculitides

9.3.5 Medically-Attended Adverse Events (MAAEs)

Special attention will be paid to recording medically-attended adverse events, which are defined as any clinical symptom or diagnosis (including local symptoms at the injection site or systemic symptoms) for which medical evaluation and/or care is sought from a qualified healthcare professional, outside of a regularly scheduled study visit. Note that MAAEs are not the same as SAEs. Whether or not an AE is an MAAE will be recorded on the appropriate Case Report Form.

9.3.6 Reporting of Pregnancy

Pregnancies occurring in study subjects will be reported on the study-specific Pregnancy Report form. No further study vaccinations will be administered to pregnant subjects, but with the subject's permission all study mandated blood samples will be obtained and the subject will continue in follow-up for safety events. Efforts will be made to follow all pregnancies reported during the course of the study to pregnancy outcome pending the subject's permission.

9.4 Type and Duration of Follow-up of Subjects after Adverse Events

AEs will be recorded if they start from the time of the first study vaccination (Day 0) up to 28 days after each dose of study product. AEs limited to new-onset chronic medical conditions will be followed through approximately 9 months after the third study vaccination (Day 380).

9.5 Halting Rules

If a dose of study vaccine is considered significantly reactogenic (see below and Section 9.2.2), dose escalation and/or additional vaccinations will be suspended until reviewed by the SMC, Independent Safety Monitor, DMID Medical Monitor, and IND sponsor (SVI). Any recommendation of the Independent Safety Monitor, DMID Medical Monitor, and SMC to resume or suspend further injections (either for an individual subject, an entire Group, or the full study) will be communicated in writing to the sponsor and Principal Investigator. All communications from the SMC will subsequently be forwarded by the investigators to the IRBs.

The following criteria will be used to define significant reactogenicity:

- One or more participants experience a protocol defined SAE that is determined to be possibly, probably, or definitely related to a study vaccine, **OR**,
- One or more participants experience a protocol defined AESI that is determined to be possibly, probably, or definitely related to a study vaccine, **OR**,
- One or more participants experience a protocol defined Grade 3 hypersensitivity reaction that is possibly, probably or definitely related to a study vaccine, **OR**,
- Two or more participants experience a protocol defined Grade 2 hypersensitivity reaction that is probably or definitely related to a study vaccine, **OR**,
- One or more participants in a single Group (i.e., Group 1, Group 2, etc.) experience the same objective physical finding or laboratory abnormality of Grade 3 or higher (with the exception of isolated Grade 3 erythema or swelling), that is determined to be probably or definitely related to a study vaccine, **OR**,
- Two or more participants in a single Group experience the same Grade 2 or higher safety laboratory abnormality or Grade 3 clinical AE that is possibly, probably or definitely related to a study vaccine.

The study will be double-blinded until all study subjects have completed their Day 140 visit, after which the Sponsor and investigators will be unblinded. During the double-blinded part of the study, a study subject's randomization code may be unblinded only for safety purposes. This is unlikely to occur, since once a vaccine is administered, knowing which vaccine was given is unlikely to influence the medical management of an AE. This procedure is therefore exceptional and any decision to unblind will be discussed with the sponsor, the Principal Investigator, the Independent Safety Monitor, and the SMC. If deemed necessary for urgent safety reasons, the Independent Safety Monitor, in consultation with the SMC (if possible in a timely manner), may unblind a specific subject without revealing the study blind to the investigators or the Sponsor. Any unblinding will be thoroughly documented. It is to be emphasized that the Independent Safety Monitor may put the study on hold at any time and discuss with the SMC. In the event that the investigators come to know the study code prior to final unblinding, the Principal Investigator must notify the Sponsor immediately. The reasons will be documented by the Principal Investigator and added to the study file.

The decision to completely unblind the study prior to Day 140 or permanently stop the study prior to Day 380 will take the form of a formal recommendation by the SMC to the study Sponsor. The Principal Investigator must then notify the IRBs of this decision.

9.6 Safety Oversight

9.6.1 Independent Safety Monitor (ISM)

An independent Safety Monitor will be appointed for oversight of subject safety in this trial. The ISM will be a local, qualified physician who will be available to advise the investigators on trial-related medical questions or problems. The ISM will work with the DMID Medical Monitor to ensure adequacy of adverse event monitoring and reporting. Should the ISM not be available, he/she will recommend an alternative to serve as a substitute ISM.

The ISM primary responsibility will be to monitor subject safety. The Principal Investigator is responsible for ensuring that the ISM is aware of any new safety information that becomes available during the course of the trial.

9.6.2 Safety Monitoring Committee (SMC)

At least three individuals will be selected to serve as the study Safety Monitoring Committee (SMC) to advise the Sponsor and the study investigators on the trial. All SMC members will be independent from the Sponsor and study site. The SMC's primary responsibility will be to monitor subject safety. The Principal Investigator is responsible for ensuring that the SMC is aware of all new safety information. The SMC will periodically review data on safety and enrollment, and will review cumulative safety data for evidence of study related AEs, adherence to the protocol, and factors that may affect outcome or study data such as protocol violations and losses to follow up.

Cumulative safety data reports from the trial will be submitted to the SMC before beginning vaccinations in Group 3 and Group 5 of the study. These safety data reports will include data from at least the first 14 days after first vaccination of all subjects in the prior Group. After the third and final vaccination has been administered to all cohorts, additional safety and immunology results and reports will be submitted to the SMC as they become available.

Conference calls between the investigators and the SMC will be scheduled at least one week prior to beginning vaccinations in Group 3 and Group 5 of the study. If no criteria for halting the study are met (see Section 9.5 above) vaccinations will proceed with approval from the SMC.

Written approval (via fax or email) to proceed to vaccinating Group 3 and Group 5 must be obtained from the SMC prior to vaccine administration. Both the SMC and ISM will have access to the randomization code, as they may wish to review the data in an unblinded fashion should significant safety questions arise prior to the final unblinding of the study.

It is the Principal Investigator's (or designated agent) responsibility to ensure that the SMC reviews the current safety data (grouped by dose cohort), study protocol, and any other requested documents at its meetings. Occurrence of an SAE will be reported to the SMC at the same time that it is reported to the IRBs. Additionally, any new information that may adversely affect the safety of the subjects or the conduct of the study will be submitted to the SMC as it becomes available.

10 CLINICAL MONITORING

10.1 Site Monitoring Plan

The Sponsor (or its designee) will monitor all aspects of the study, with respect to current Good Clinical Practices, and for compliance with applicable government regulations. Prior to the start of the study, the Principal Investigator will be informed of the frequency of monitoring visits and will be given reasonable notification prior to each visit. The objectives of a monitoring visit will be to verify the prompt reporting of SAEs, to check the availability of the signed Informed Consent for enrolled study subjects, to compare CRFs and spreadsheets with source data for completeness and accuracy, to verify compliance with the clinical protocol, and to check investigational product accountability. During the monitoring visit, the Principal Investigator (and/or designee) and other study personnel should be available to discuss the study. Study documents must be available for review throughout the course of the study.

11 STATISTICAL CONSIDERATIONS

11.1 Study Hypotheses

This study is not designed to statistically test a specific hypothesis. Rather, it is intended to assess the safety, reactogenicity, and immunogenicity of two novel vaccines being co-administered to humans for the first time. The chosen sample size principally facilitates the assessment of safety, as discussed in Section 11.2, *Sample Size Considerations*. Given that, this study will explore, primarily by using descriptive statistics, to assess the following hypotheses:

1. Co-administration of the Na-APR-1 (M74)/Alhydrogel[®] and Na-GST-1/Alhydrogel[®] vaccines will not increase the reactogenicity or safety risk above that of either administered alone.
2. Co-administration of the Na-APR-1 (M74)/Alhydrogel[®] and Na-GST-1/Alhydrogel[®] vaccines will not decrease the functional activity of induced IgG antibodies to either antigen compared to when either is administered alone.
3. Co-administration of the Na-APR-1 (M74)/Alhydrogel[®] and Na-GST-1/Alhydrogel[®] vaccines will not decrease the IgG antibody response to either antigen compared to when either is administered alone.
4. Co-administration of the Na-APR-1 (M74)/Alhydrogel[®] and Na-GST-1/Alhydrogel[®] vaccines will not decrease the avidity of induced IgG antibodies to either antigen compared to when either is administered alone.
5. Co-administration of the Na-APR-1 (M74)/Alhydrogel[®] and Na-GST-1/Alhydrogel[®] vaccines will not decrease the induction of specific MBCs to either antigen compared to when either is administered alone.

11.2 Sample Size Considerations

This Phase 1 trial is not powered to detect statistically significant differences between groups. Even though comparative statistics for the safety variables will be computed, the study will have low power to detect anything other than very large differences in the incidence of local injection site and systemic side effects between the vaccination groups. This is done weighing the need to detect any possible untoward reactions against the need to limit the number of volunteers involved for safety purposes. The sample size of 60 for this study is within the range commonly used in Phase 1 trials for the initial assessment of the safety, tolerance and immunogenicity of investigational vaccines.

The primary objective of the study is to estimate the frequency of vaccine-related adverse events. Therefore, rather than providing a statistical power calculation for a specific hypothesis, we illustrate below the probability of observing one or more events, such as an adverse event of a particular type, for a single vaccine dose (N=20), formulation (N=30), or for all participants (N=60) under different assumptions of the true rate at which such events occur in the population.

	Probability of Observing 1 or More Events		
	N=20	N=30	N=60
"True" (but unknown) Probability of an Event			
0.5%	9.54%	13.96%	25.97%
1.0%	18.21%	26.03%	45.28%
3.0%	45.62%	59.90%	83.92%
5.0%	64.15%	78.54%	95.39%
10.0%	87.84%	95.76%	99.82%

As illustrated in the table above, the study will have high probability ($\geq 80\%$) of detecting events that are commonly occurring in the population. For example, with a sample of 20 participants (which is equivalent to the size of each dose group of *Na*-APR-1 (M74) in this study), there is an 87.84% probability of observing 1 or more events when the events occur at a rate of 10.0% in the population. As the sample size increases, the study is able to detect events that occur at lower rates. For example, using a sample size of 30 participants (which is equivalent to the number of participants assigned to vaccine co-administration in this study vs. *Na*-APR-1 (M74) alone), there is a 78.54% probability of observing 1 or more events that occur at a rate of 5% in the population. Using a sample of size 60 (equivalent to the entire study population) there is an 83.92% probability of observing 1 or more events that occur at a rate of 3% in the population. Detection of rare events—those that occur at a rate of 1% or less in the population—is not likely in this study.

11.3 Planned Interim Analyses

11.3.1 Safety Review

Descriptive and hypothesis-testing approaches will be used to estimate AE rates and to compare these rates in the difference doses and formulations of *Na*-APR-1 (M74) alone or co-administered with *Na*-GST-1. Estimates will be presented with their 95% confidence intervals. Formal statistical tests, as outlined below, will be used to compare doses. No formal adjustments for multiple comparisons will be made. Statistical tests will use a two-sided significance level of 5%.

The proportion of subjects with at least one injection site AE will be compared by vaccine allocation (e.g., *Na*-APR-1 (M74) vs. *Na*-APR-1 (M74) co-administered with *Na*-GST-1), by *Na*-APR-1 (M74) dose, and by GLA-AF dose.

Laboratory results (hematological and clinical chemistry) will be examined for trends over time and any clinically significant values for individuals will be reported.

11.3.2 Immunogenicity Review

The proportion of subjects with detectable anti-*Na*-GST-1 and anti-*Na*-APR-1 (M74) responses, and the duration of responses, will be summarized as descriptive measures. Geometric mean antibody responses will be compared between Groups with comparisons made by analysis of variance (ANOVA) tests and pair-wise comparisons by contrasts. Antibody responses will be measured at Days 0, 7, 14, 28, 56, 63, 70, 84, 112, 119, and 126 for interim analysis, with Days 140, 200, 290, and 380 added for final analysis.

To exploit the multiple measures of antibody within each subject, a longitudinal model may be built (if possible) to describe the antibody responses over time. The models will explore if there are any differences between those administered *Na*-APR-1 (M74)/Alhydrogel[®] alone and those co-administered *Na*-GST-1/Alhydrogel[®].

Summary statistics will be used to present exploratory study results of the cellular immune responses to *Na*-GST-1 and *Na*-APR-1 (M74) before and after immunization. To assess the changes in lymphocyte proliferative responses and cytokine/chemokine profiles over time, a generalized estimating equations model with robust standard errors will be constructed. When necessary, data reduction approaches will be used.

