2.2.3 Clinical Development Plan for the Human Hookworm Vaccine

The target population for the human hookworm vaccine is children less than 10 years of age living in hookworm endemic areas, since this is the age group that is most at risk of disease from this infection. Prior to conducting clinical trials in this age group, however, both *Na*-GST-1 and *Na*-APR-1 (M74) are being tested in healthy adults living in areas of high hookworm prevalence.

The decision to proceed to Phase 1 testing in children will be taken after the investigators, the Safety Monitoring Committee (SMC), and the Sponsor have reviewed an interim report of the study described in this protocol. This interim report will include the safety and immunogenicity data of all subjects following three immunizations. It is anticipated that the interim report will be available for review in early 2016. Assuming that co-administration of the two antigens in adults does not result in significant safety concerns, testing will proceed to a Phase 1 trial in Brazilian children living in a hookworm endemic area. After safety and immunogenicity of the co-administered products is shown in children, testing of a co-formulated product that contains both *Na*-GST-1 and *Na*-APR-1 (M74) will be started, first in adults and then in children. The dose concentrations and components of the co-formulated product will be determined through the cumulative results of the study described in this protocol and the previous Phase 1 trials of these vaccine antigens.

Besides the vaccine co-administration trial described in this protocol, a second Phase 1 trial to assess the safety and immunogenicity of co-administration of *Na*-APR-1 (M74) and *Na*-GST-1

in healthy adults in a hookworm-endemic region of Gabon is also being planned, with anticipated initiation in late 2014. A 0, 28 and 180-day (0, 1 and 6 months) vaccine schedule is being evaluated in the Gabon study, as compared to the 0, 56, and 112-day (0, 2 and 4 months) vaccination schedule evaluated in this protocol. Results from the studies in Gabon and Brazil will be compared to evaluate co-administration safety and immune interference in diverse hookworm-exposed populations, and to decide on antigen doses, formulations, and vaccination schedule to be used in future clinical trials.

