4 STUDY DESIGN

The study will be conducted as a randomized, placebo-controlled, double-blind Phase 1 dose-escalating clinical trial in healthy adult volunteers living in the hookworm-endemic area of Americaninhas, Brazil.

Prior to beginning study-related activities, the consent and cooperation of local municipal government leaders and representative community members will be sought, after which volunteers will be invited to participate in the study. After providing written informed consent and passing the informed consent comprehension questionnaire, volunteers will undergo eligibility screening, including a complete medical history, physical examination, hematology testing, serum glucose testing, liver and renal function testing, HIV antibody testing, Hepatitis B and C serology, and urinalysis; urine pregnancy testing will be performed on all female volunteers. In addition, all volunteers will be tested for serum IgE antibodies to *Na*-APR-1 (M74) and *Na*-GST-1, and a fecal examination will be performed for ova and parasites. All clinically significant abnormalities will be reviewed with volunteers and referral for follow-up care will be provided. After screening, those volunteers determined to be eligible, based on the inclusion and exclusion criteria, will be invited to participate in the study.

Sixty volunteers will be progressively enrolled into 1 of 6 Groups over a projected 3-month enrollment period, with each subject followed for 13 months post-enrollment (to Study Day 380). Group enrollment will be done in an open sequential fashion, whereas within each Group, investigational product (IP) assignment and vaccination will be done in a randomized double-blind fashion.

The first 20 subjects will be entered into Groups 1 and 2

- Group 1 double-blind IP assignment (n=10):
 - 5 subjects will receive 10µg *Na*-APR-1 (M74) delivered by IM injection in the deltoid muscle, with sterile saline administered to the alternate arm.
 - 5 subjects will receive 10µg *Na*-APR-1 (M74) delivered by IM injection in the deltoid muscle, with 100µg *Na*-GST-1 administered to the alternate arm.
- Group 2 double-blind IP assignment (n=10):
 - 5 subjects will receive 10µg *Na*-APR-1 (M74) plus 5µg GLA-AF delivered by IM injection in the deltoid muscle, with sterile saline administered to the alternate arm.

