15.4 Timing/Reports

In addition to the study-related documentation required by the regulatory authorities, 4 study reports will be generated. These include 2 interim SMC safety reports, 1 interim safety and immunogenicity study report, and the final study report. The first interim SMC safety report will be completed after the safety data from the Day 14 visits of Group 2 have been compiled, for the purposes of deciding whether it is safe to precede with enrollment into Group 3 of the study. The second interim SMC safety report will be completed after the safety data from the Day 14 visits of Group 4 have been compiled, for the purposes of deciding whether it is safe to precede with enrollment into Group 5 of the study. The interim study report will be compiled after interim safety and primary immunogenicity data (i.e., antigen-specific IgG responses to *Na*-GST-1 and *Na*-APR-1 (M74) as determined by ELISA) from all Day 140 visits is available and the study investigators unblinded. This report will serve as the basis for deciding whether to continue with

future Phase 1 testing of the vaccines in children. A final report containing all safety and immunology data will be prepared after trial completion.

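### The fixed interim IgG comparison in Section 11.3.2 is between Groups 1-6, so it averages over the randomised Na-GST-1 allocation and leaves the co-administration contrast optional

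*Protocol*

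**What the plan says.** The interim IgG comparison in Protocol Section 11.3.2 reads: "Geometric mean antibody responses will be compared between Groups with comparisons made by analysis of variance (ANOVA) tests", to which the same sentence adds pair-wise contrasts. Alone versus co-administered is named one paragraph later, as something the longitudinal modelling would explore, and that modelling is conditional: "a longitudinal model may be built (if possible) to describe the antibody responses over time". The section also provides for descriptive response proportions and durations, and for summary statistics with a GEE model of cellular responses. None of these names co-administration status.

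The capitalised word Group has a settled meaning. Section 4 says: "Sixty volunteers will be progressively enrolled into 1 of 6 Groups". The halting rules in Section 9.5 use it in the same way: "One or more participants in a single Group (i.e., Group 1, Group 2, etc". The six Groups are the combinations of Na-APR-1 dose (10, 30, 100 µg) and GLA-AF (none, 5 µg), ten people each, filled in open sequence. Inside each Group, five receive saline and five Na-GST-1. Section 5.3.2 places both the random allocation and the blind there.

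On timing, Section 11.3.2 ends the interim antibody series at Day 126, "with Days 140, 200, 290, and 380 added for final analysis". Section 15.4 compiles the interim report once ELISA IgG data "from all Day 140 visits is available and the study investigators unblinded". Sections 5.3.2 and 15.4 tie that report to the decision on paediatric trials. Section 2.2.3 words the condition for proceeding as: "Assuming that co-administration of the two antigens in adults does not result in significant safety concerns".

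**The concern.** The trial asks whether giving Na-GST-1 alongside Na-APR-1 lowers the response to either antigen (Section 2.2.1; hypothesis 3 in Section 11.1; the secondary objective). Its randomised evidence for anti-Na-APR-1 is saline versus Na-GST-1 within Group. A comparison between Groups contrasts dose and adjuvant cohorts that were not randomised against each other, and it mixes both randomised halves in every mean. Read literally, an interim report could satisfy Section 11.3.2 without any estimate of the effect of co-administration on IgG.

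The neighbouring sections do name the comparison. Section 11.3.1 compares injection-site events by vaccine allocation, and Section 11.4 (secondary analysis, items d to f) makes Na-GST-1 status a factor. The gap is confined to the interim immunogenicity review.

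Unblinding makes it matter more. Dose and GLA-AF are open throughout, so Groups can be compared without breaking any code. What investigators learn after Day 140 is who received Na-GST-1. The plan gives up that blind early while leaving optional the IgG comparison that needs it.

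For anti-Na-GST-1 IgG, a Group mean also averages people who received the antigen with people who did not.

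**Working it through.** **The plan's own figure.** The only design calculation is the table in Section 11.2, 1 − (1 − p)^n. For example, 1 − 0.90^20 = 87.84%. All 15 cells reproduce. The table concerns adverse events and does not bear on this point.

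**Inputs.** From the protocol: 6 Groups of 10, split 5:5; two-sided 5% level (stated in Section 11.3.1). Not given, hence assumed: a co-administration effect d of 0.5 to 1.5 SD of log IgG, no dose or GLA-AF effect, and all 60 subjects evaluable at Day 126.

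**Step 1: what the between-Group ANOVA sees.** The 5:5 split shifts every Group mean by the same d/2, so the between-Group sum of squares carries no signal. The effect goes into the error term. With unit variance, the expected within-Group mean square is [54 + 6 × 10 × (d/2)²]/54 = 1 + 0.278d², that is 1.07, 1.28 and 1.63 for d = 0.5, 1.0 and 1.5. The test therefore becomes less likely to reject as the effect grows. Pair-wise contrasts between Groups cancel the effect in the same way.

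**Step 2: simulation and power.** ANOVA columns: 20,000 simulated trials per effect size, with 5 and 54 df for six Groups. Last column: noncentral t for a Group-stratified contrast with 53 df.

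| d (SD) | ANOVA, 6 Groups | ANOVA, 12 randomised cells | 30 v 30, Group-adjusted |
|---|---|---|---|
| 0 | 5.1% | 5.1% | – |
| 0.5 | 3.8% | 16% | 48% |
| 1.0 | 1.7% | 64% | 97% |
| 1.5 | 0.4% | 97% | >99% |

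The 12-cell column shows what would follow if Groups meant the randomised cells, a reading that the definition of Group does not support.

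**Step 3: precision of the missing contrast.** The 95% CI half-width for 30 v 30 is t(53) × √(2/30) = 2.006 × 0.258 = 0.52 SD of log IgG. If the SD of log10 IgG were 0.3, 0.4 or 0.6 (assumed), the half-width would be 0.156, 0.208 or 0.312 log10. The geometric mean ratio would then be known to within a factor of 1.4, 1.6 or 2.1 either way.

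**Step 4: anti-Na-GST-1 averaged over a Group.** If recipients exceed non-recipients F-fold, the Group geometric mean understates that of recipients by √F: 3.2-fold for F = 10 and 10-fold for F = 100 (F assumed). The pooled SD is √(s² + (log10 F / 2)²). For s = 0.4 it is √(0.16 + 0.25) = 0.64 when F = 10 and √(0.16 + 1) = 1.08 when F = 100. For s from 0.3 to 0.6 the ranges are 0.58 to 0.78 and 1.04 to 1.17.

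**Step 5: timing, side by side.** Section 11.3.2 assigns Day 140 IgG to the final analysis. Section 15.4, read literally, waits for IgG data from the Day 140 visits. Section 5.3.2 requires that Day 140 visits be complete and that safety and secondary immunogenicity outcomes be entered, and Section 3.2.2 sets those secondary outcomes at Day 126. Section 9.4 closes general AE recording 28 days after a dose, which is Day 140 for dose 3. On that reading Day 140 is a visit and safety trigger, and Day 126 is the IgG endpoint.

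**The case against.** The strongest reply is that this is loose drafting which the analysis plan would settle. Section 11.4 promises a detailed plan, the secondary outcomes are defined by co-administration status, and unblinding the allocation makes little sense unless that comparison is intended. Much of this is fair as to intent. But the protocol does not leave the comparison open: it names one that cannot answer the question and makes the one that can conditional.

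A second reply is that the trial is descriptive and not powered (Sections 11.1 and 11.2). That stands, and the power figures above only illustrate sensitivity. An estimate with a confidence interval suits a descriptive trial.

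A reader might also infer more than the text supports:

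- **That interim IgG decides on paediatric testing.** The report also carries safety data, and the go condition in Section 2.2.3 is a safety one. The IgG result informs the decision; no immunogenicity gate is stated.
- **That an ANOVA is all Section 11.3.2 fixes.** It also fixes contrasts, descriptive summaries and a cellular-response model.
- **That needed data are left out because IgG stops at Day 126.** The secondary endpoint is Day 126 and is in the interim set. Section 15.4 is ambiguous, which calls for clarification and does not justify a second lead time point.
- **That duration of response cannot be described by Day 126.** Samples on Days 28, 56, 84 and 112 show persistence after doses 1 and 2.

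**Conclusion.** The point holds for the interim immunogenicity review. Section 11.3.2 fixes a comparison between six non-randomised cohorts and leaves the randomised alone-versus-co-administered comparison of IgG optional. Under the stated assumptions the fixed ANOVA is insensitive to a co-administration effect, rejecting in 3.8% of trials at 0.5 SD and 0.4% at 1.5 SD. The adjusted 30 v 30 contrast estimates that effect to within ±0.52 SD. That the effect cancels in Group means follows from the balanced 5:5 split and needs no assumption about SD; the percentages depend on the assumed effects and complete data. Enrolled subjects who leave are not replaced (Section 5.3.1), so losses would widen the interval and could leave Groups slightly unbalanced.

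The final analysis is unaffected, because Section 11.4 already includes Na-GST-1 status. The Day 140 wording is a smaller, separate matter of reconciling Section 15.4 with Sections 5.3.2 and 11.3.2.

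**What to change.** In Section 11.3.2:

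1. Make the lead interim analysis a Day 126 log-IgG model with Na-GST-1 status as a factor, adjusted for Group (or for Na-APR-1 dose and GLA-AF, as in Section 11.4, secondary analysis, items d and e). Report the anti-Na-APR-1 geometric mean ratio, co-administered over alone, with its 95% CI. Between-Group comparisons can follow as supporting description.
2. Do not average anti-Na-GST-1 IgG over saline and Na-GST-1 recipients; summarise it in recipients. A summary in recipients alone cannot show interference with that antigen, so state whether the SVI-10-01 specimens from people given Na-GST-1 without Na-APR-1 serve as comparator at interim. Section 11.4 brings them in only for the analyses that follow it. The comparison would be historical, not randomised, and should be labelled so.
3. Reconcile the timing with Section 15.4: say whether Day 140 is the visit and safety trigger, with IgG to Day 126, or an interim IgG time point.

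The cost is wording and slightly more interim analysis work. No subjects, visits or blood draws are added. If the SVI-10-01 specimens are used at interim, their assays must be ready by then, since Section 11.4 has them run alongside the new samples.
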